
Presentation of results

 ● Adjusted geometric means, the mean difference between each dose (test) and the placebo (reference) at each timepoint and associated 95% confidence interval will be constructed using the residual variance. ● The treatment ratios and 95% CI will be calculated by back-transforming the difference between the least square means and associated 95% CI. ● Percentage change from baseline at each timepoint will be calculated from the adjusted geometric means using the formula $100\% \times (\exp(\text{adj mean}) - 1)$.

Pathway and Target Engagement

Endpoints

 ● $\text{Log Ratio} = \text{Log}(\text{free TEAR1}) - \text{log}(\text{total TEAR1})$.

Model Specification

 ● A mixed effect model will be fitted with randomised treatment, time (i.e. planned relative time) and randomised treatment * time as a fixed effect and participant as a random effect. Baseline log ratio will be fitted as a continuous covariate along with Baseline log ratio* time. ● The Kenward and Roger method for approximating the denominator degrees of freedom and correcting for bias in the estimated variance-covariance of the fixed effects will be used. ● An unstructured covariance structure for the R matrix will be used by specifying 'type=UN' on the REPEATED line with a subject=SUBJID option.

Model Checking

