
 ● For the MMRM, model assumptions will be applied, but appropriate adjustments may be applied based on the data. ● In the unlikely circumstance that there are convergence problems with the MMRM analysis, this will be explored. For example, the SCORING=4 option could be used in the MIXED statement, which makes SAS use Fisher scoring for the first 4 iterations. If the convergence problem cannot be resolved, the unstructured covariance matrix will be replaced by ANTE (1) covariance structure in combination with a random participant effect. ● If this model fails to converge, alternative correlation structures may be considered such as CSH or CS. ● Distributional assumptions underlying the model used for analysis will be examined by obtaining a normal probability plot of the residuals and a plot of the residuals versus the fitted values (i.e. checking the normality assumption and constant variance assumption of the model respectively) to gain confidence that the model assumptions are reasonable. ● If there are any departures from the distributional assumptions, alternative models will be explored using appropriate transformed data.

Pathway and Target Engagement
Presentation of Results

 Adjusted geometric means, the mean difference between each dose (test) and the placebo (reference) at each timepoint and associated 95% confidence interval will be constructed using the residual variance. The treatment ratios and 95% CI will be calculated by back-transforming the difference between the least square means and associated 95% CI. Percentage target engagement at each timepoint will be calculated from the adjusted geometric means using the formula: $100\% \times (\exp(\ln(v_2 / v_1) + 1))$ percentage target engagement = $(1 - \text{engagement ratio}) * 100$.

Transcriptomics – Fold Change Analysis

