12.6.5. Biomarker

TEAR

Target Engagement
 
 • Ratio = free / total • Target Engagement = $100 - (\text{ratio}_{\text{post}} / \text{ratio}_{\text{baseline}}) * 100$ • BIOMARK dataset: BICAT = TRIPK1 (total) or FRIPK1 (free) and BITESTCD = CONC

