12.10.11. Pharmacodynamic and/or Biomarker Tables

Pharmacodynamic and Biomarker: Tables					
No.	Population	IDSL / Example Shell	Title	Programming Notes	Deliverable [Priority]
Exploratory Biomarkers					
6.1.	Safety	PD_T1	Summary Statistics for Actual and Percentage Change from Baseline in Biopsy Tissue Inflammatory Biomarkers (Parts A and B)	One page for each cell type/measure by visit/time and treatment	SAC [1]
6.2.	Safety	PD_T2	Adjusted Mean (95% CI) of Percentage Change from Baseline in Biopsy Tissue Inflammatory Biomarkers (Parts A and B)	One page for each cell type/measure by visit/time and treatment/dosing regimen	SAC [1]
Pathway and Target Engagement					
6.3.	Safety	EFF_T1	Summary Statistics for Observed TEAR1 % Target Engagement (Parts A and B)	Separate summaries for sample type (Blood/Biopsy) % Target Engagement by visit/time	SAC [1]
6.4.			Summary Statistics for Predicted TEAR1 % Target Engagement based on predicted GSK2982772 trough concentrations (Parts A and B)		
6.5.	Safety	PD_T3	Adjusted Mean (95% CI) of TEAR1 % Target Engagement in Blood (Parts A and B) by Randomised Treatment		SAC [1]
6.6.	Safety	PD_T3	Adjusted Mean (95% CI) of TEAR1 % Target Engagement in Biopsy Tissue (Parts A and B) by Randomised Treatment		SAC [1]
6.7.	Safety	EFF_T1	Summary Statistics of Pathway Engagement (Parts A and B) by Randomised Treatment	Separate summaries for sample type (Blood/Biopsy)	SAC [1]
6.8.	Safety	PD_T3	Adjusted Mean (95% CI) of Pathway Engagement in Blood (Parts A and B) by Randomised Treatment		SAC [1]
6.9.	Safety	PD_T3	Adjusted Mean (95% CI) of Pathway Engagement in Biopsy Tissue (Parts A and B) by Randomised Treatment		SAC [1]

Pharmacodynamic and Biomarker: Tables					
No.	Population	IDSL / Example Shell	Title	Programming Notes	Deliverable [Priority]
mRNA Expression					
6.10.	Safety	PD_T4	Summary of mRNA Expression of Inflammatory Gene Transcripts (Parts A and B) by Randomised Treatment	Separate summaries for sample type (Blood/Biopsy) qPCR – micarray dataset	SAC2 [1]
6.11.	Safety	PD_T5	Frequency Table Summarising the Number of Probe Sets with Various Fold Change (Parts A and B) by Randomised Treatment	Separate summaries for sample type (Blood/Biopsy). Use cut-offs 1.5 and -1.5 initially. Change to -1.25 and 1.5 if no one achieves the initial cut-offs	SAC2 [1]

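### Section 10.1.3.1 gives two conflicting conversions of the modelled TEAR1 log ratio to percentage target engagement, with undefined terms and no stated baseline reference

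*SAP*

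**What the plan says.** Section 12.6.5 of the SAP starts from "Ratio = free / total" and defines target engagement as 100 minus 100 times the post-dose ratio divided by the baseline ratio. No engagement is therefore 0% and full engagement is 100%.

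Section 10.1.3.1 (Pathway and Target Engagement) models a different quantity. The response is log(free TEAR1) − log(total TEAR1), with no baseline subtracted. Baseline enters on the right-hand side only: "Baseline log ratio will be fitted as a continuous covariate along with Baseline log ratio* time".

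Under Presentation of Results the section continues: "Percentage target engagement at each timepoint will be calculated from the adjusted geometric means using the formula". Two expressions follow in the same bullet:

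- Expression 1: 100% × (exp(ln(v2/v1) + 1)).
- Expression 2: percentage target engagement = (1 − engagement ratio) × 100.

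The bullet does not say what v1, v2 or the engagement ratio are, or how the two expressions connect. The result goes into displays such as Table 6.5, "Adjusted Mean (95% CI) of TEAR1 % Target Engagement in Blood (Parts A and B) by Randomised Treatment", its biopsy counterpart Table 6.6, and Figures 6.4 and 6.5.

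**The concern.** The plan defines percentage target engagement once, in 12.6.5, and the modelled displays should be on that scale. Expression 1 does not have the form of that definition, and expression 2 has it only under one reading of an undefined term. If the modelled values do not follow 12.6.5, Tables 6.5 and 6.6 would carry the same percentage label as the observed summary in Table 6.3 but could not be compared with it. A placebo arm whose free/total ratio had not moved could also show apparent engagement. As it stands, two programmers could follow the bullet and produce different numbers.

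**Working it through.** **Inputs.** All formulas come from SAP Sections 10.1.3.1 and 12.6.5. The plan gives no TEAR1 values, so the ratios below are illustrative assumptions.

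**Step 1: read v2/v1 and the engagement ratio as post-dose/baseline = R.**

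- Section 12.6.5: 100 × (1 − R).
- Expression 1 as printed: 100 × exp(ln R + 1) = 100 × e × R.
- Expression 1 with the 1 outside the exponential: 100 × (R + 1).
- Expression 2: 100 × (1 − R).

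| R | 12.6.5 | Expr. 1 as printed | Expr. 1, other bracket | Expr. 2 |
|---|---|---|---|---|
| 1 | 0% | 271.8% | 200% | 0% |
| 0.5 | 50% | 135.9% | 150% | 50% |
| 0.25 | 75% | 68.0% | 125% | 75% |
| 0.1 | 90% | 27.2% | 110% | 90% |

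Under both bracketings expression 1 falls as engagement rises. As printed it exceeds 100% whenever R > 1/e = 0.368; in the other bracketing it does so for every positive R. Expression 2 agrees with 12.6.5 throughout.

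**Step 2: can expression 1 be rescued?**

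- Changing + 1 to − 1 outside the exponential gives 100 × (R − 1) = 0, −50, −75, −90%, the negative of 12.6.5.
- Using expression 1 (without the 100%) as the engagement ratio in expression 2 gives −171.8, −35.9, 32.0, 72.8% as printed, or −100, −50, −25, −10% with the other bracket. Direction is restored, but the values are wrong.

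**Step 3: apply expression 2 to what the model produces.** The response is the visit log ratio, so its back-transformed adjusted mean is a free/total ratio at the visit. Fitting baseline as a covariate adjusts that mean but does not divide it by baseline. Two other places in the SAP support this reading. Table 8 lists the statistical analysis of target engagement under Absolute, but that of the inflammatory biomarkers under Change from Baseline. For those biomarkers, Section 10.1.3.1 explicitly subtracts the log baseline and pairs the result with 100% × (exp(adjusted mean) − 1).

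With a baseline free/total of b and no change, 12.6.5 gives 0%. Expression 2 applied to the visit ratio gives 100 × (1 − b):

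| Assumed b | No change (12.6.5: 0%) | Ratio halved (12.6.5: 50%) | Ratio cut to a tenth (12.6.5: 90%) |
|---|---|---|---|
| 1.0 | 0% | 50% | 90% |
| 0.9 | 10% | 55% | 91% |
| 0.8 | 20% | 60% | 92% |
| 0.6 | 40% | 70% | 94% |

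The discrepancy vanishes only at b = 1. For b below 1 it is largest where engagement is least, that is, in an untreated arm.

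**The case against.** A reader might infer that the whole conversion rule is reversed and exceeds 100%. The text does not support that. Those faults belong to expression 1; expression 2, in the same bullet, has the right direction and cannot exceed 100% for a positive ratio.

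Expression 1 may also be a typing or text-extraction fault. A lost leading minus with a displaced bracket, 100% × (−exp(ln(v2/v1)) + 1), would equal 100 × (1 − v2/v1). That would agree with 12.6.5 if v2/v1 is post over baseline, and would explain why the two expressions stand together. This cannot be settled from the extracted text, so the 272% and 200% describe the formula as printed.

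A reader might also conclude that the modelled engagement is definitely not referenced to baseline. That is a strong inference, not a stated fact. The engagement ratio is undefined, v2/v1 reads naturally as post over baseline, and the only derivation of engagement elsewhere in the plan uses that ratio. What stands is that the bullet computes the percentage from adjusted geometric means, and the specified model yields those as visit free/total ratios.

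Finally, it would go too far to say that the trial could not tell whether the target was engaged. The endpoint is exploratory and depends on evaluable samples (Section 2.2). Observed engagement has its own derivation, and the treatment ratios with their intervals are specified separately as back-transformed differences in least-squares means.

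**Conclusion.** The point holds as an internal inconsistency with undefined terms. Expression 1 as printed cannot be reconciled with 12.6.5 under either bracketing. Expression 2 can be, but only if the engagement ratio is post-dose over baseline; the SAP does not say so, and its model does not deliver that ratio. Taken literally, the modelled percentage has no baseline reference and overstates engagement by up to 100 × (1 − b) points when baseline free/total b is below 1: 20 points at an assumed 0.8, none at 1. The size in this trial is unknown because no TEAR1 values are given. The reach is limited to the percentage scale of Tables 6.5 and 6.6 and Figures 6.4 and 6.5. It is worth correcting before programming, but touches neither the primary safety objective nor any treatment comparison.

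**What to change.** - Check expression 1 against the source PDF, then delete it.
- Define the engagement ratio as exp(D), where D is the adjusted mean change from baseline in log ratio. Obtain D by modelling visit minus baseline log ratio with the same terms. Equivalently, keep the current response and subtract the mean baseline log ratio at which the adjusted means are evaluated; state which is used.
- Report 100 × (1 − exp(D)). For R = exp(D) = 1, 0.5, 0.25, 0.1 this gives 0, 50, 75, 90%, as in 12.6.5.
- State that the confidence limits swap. If D has limits L < U, the lower limit for engagement is 100 × (1 − exp(U)) and the upper is 100 × (1 − exp(L)).

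The cost is one formula and one definition. Because baseline and baseline-by-time are already in the model, the treatment contrasts do not change. No new data are needed, and the modelled displays then share the 12.6.5 scale with Table 6.3.

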
 The \log_2 normalised copy numbers (also referred to as $\log_2(\text{intensity})$) received from the normalised process will be listed and summarised appropriately by randomised treatment. As the data will be \log_2 transformed prior to the analysis, the randomised treatment effects will be expressed as ratios after back transformation to the original scale. These ratios can be converted from randomised treatment ratios to fold change values as follows: 
 If ratio ≥ 0 then fold change = ratio If ratio < 0 then fold change = $-1/\text{ratio}$
Endpoint(s)

 $\log_2(\text{intensity})$ mRNA expression of inflammatory gene transcripts
Model Specification

 Endpoints will be statistically analyzed using a linear repeated measure mixed effects model. Terms fitted in the linear repeated measures mixed effects model will include: 
 Fixed Category : Treatment, Visit, Treatment * Visit Random Effect : Participant
Model Checking & Diagnostics

 Model assumptions will be applied, but appropriate adjustments may be applied based on the data. In the unlikely circumstance that there are convergence problems with the analysis, this will be explored. If this model fails to converge, alternative correlation structures may be considered such as CSH or CS. Distributional assumptions underlying the model used for analysis will be examined by obtaining a normal probability plot of the residuals and a plot of the residuals versus the fitted values (i.e. checking the normality assumption and constant variance assumption of the model respectively) to gain confidence that the model assumptions are reasonable. If there are any departures from the distributional assumptions, alternative models will be explored using appropriate transformed data.
Presentation of Results

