
 For each probeset analysed adjusted means with corresponding 95% CI and fold changes with corresponding 95% CI's can be outputted. The fold change is derived from the ratio of the back-transformed estimate of the difference between adjusted means. Plots of LS means and 95% confidence intervals from the model will be generated for each treatment by time. Additionally, plots of differences and 95% confidence intervals for the comparison between the treatment groups will be generated. For each comparison subsets of probesets will be identified based on an appropriate fold-change, for example, fold changes >1.5 or <-1.5. The proportion of probesets with fold changes >1.5 or <-1.5 will

Transcriptomics – Fold Change Analysis

be summarised in a frequency table.

- Exploratory graphical reporting on the back-transformed scale can include:
 - \log_2 (intensity) plotted against time point separately for individual participants, grouped by randomised treatment group
 - Adjusted mean intensity and 95 CI% plotted by treatment group and time point.

Transcriptomics - MicroArray RNA Analysis

- MicroArray RNA will be extracted and hybridised using a balanced batch design by Epistem. An appropriate microarray platform will be determined at the time of hybridisation, to allow for improvements in technology. The quality of the data will be assessed and then normalised using appropriate methodologies and software.
- Microarray mRNA data will be normalised using gcRMA or RMA in Array Studio v5.0 or later. After normalisation, the data will be quality assessed and any samples deemed as QC fails will be excluded from any further analysis. This quality assessment will involve looking for outlying signals in both the normalised expression data and the MAS5 QC metrics generated from each sample. If any samples are excluded, the remaining data will be re-normalised. The output from the normalisation will be \log_2 transformed mRNA intensity data (measured in arbitrary units).
- Microarray data consists of expression values (\log_2 -transformed) derived from individual probesets designed against coding regions of individual genes. More than one probeset can exist per gene. This analysis will be conducted at the probeset level.

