- To compare the percentage inhibition for each selected probeset, the following linear repeated measures mixed effects model will be fitted to each selected probeset, with percentage inhibition as the response variable. Randomised Treatment by visit, randomised treatment and visit will be fitted as fixed effects and participant as a random effect. Example SAS code is given below:

```
proc mixed data=data;
class subjid treatment visit;
model perinhibit= treatment visit treatment*visit /ddfm=kr;
repeated visit / subject=subjid type=un;
lsmeans treatment*visit / diff cl alpha=0.05;
run;
```

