6.12.	Safety	PD_T6	Summary of Adjusted Mean Fold Changes in mRNA Expression of Inflammatory Gene Transcripts (Parts A and B) by Randomised Treatment	Separate summaries for sample type (Blood/Biopsy). If Adj Mean FC lies between -1 and 1 then do not include on table	SAC2 [1]
6.13.	Safety		Summary of Analysis for Microarray mRNA Intensity Data in Blood	GSK to produce Only to be produced for significant probsets based on adjusted p-values. If Adj Mean FC lies between -1 and 1 then do not include on table	SAC2 [1]
6.14.	Safety		Summary of mRNA Percentage Inhibition of Inflammatory Gene Transcripts in Blood	GSK to produce Only to be produced for significant probsets based on adjusted p-values.	SAC2 [1]

Pharmacodynamic and Biomarker: Tables					
No.	Population	IDSL / Example Shell	Title	Programming Notes	Deliverable [Priority]
6.15.	Safety		Summary of Analysis for Microarray mRNA Percentage Inhibition Data in Blood	GSK to produce Only to be produced for significant probsets based on adjusted p-values. If Adj Mean FC lies between -1 and 1 then do not include on table	SAC2 [1]

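### The fold-change rule splits at 0 instead of 1, so no negative fold change can arise and the -1 to 1 filter drops every ratio below 1 from Tables 6.12 and 6.13 (exploratory, minor)

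*SAP*

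**What the plan says.** SAP Section 10.1.3.1 (Transcriptomics – Fold Change Analysis) models log2 intensity, and "the randomised treatment effects will be expressed as ratios after back transformation to the original scale". It then gives a two-branch conversion from ratio to fold change. The first branch is "If ratio ≥ 0 then fold change = ratio"; the second, for a ratio below 0, is -1/ratio. The presentation paragraph confirms which quantity enters the rule: "The fold change is derived from the ratio of the back-transformed estimate of the difference between adjusted means".

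The same section selects probesets with a fold change above 1.5 or below -1.5, given as example cut-offs. In Section 12.10.11 the programming note for Table 6.11 reads "Use cut-offs 1.5 and -1.5 initially" and continues "Change to -1.25 and 1.5 if no one achieves the initial cut-offs". Tables 6.12 (blood and biopsy) and 6.13 (blood) carry the note "If Adj Mean FC lies between -1 and 1 then do not include on table". Table 6.13 also carries "Only to be produced for significant probsets based on adjusted p-values". In Section 12.10.12, Figure 6.19 is to be drawn with a shaded band from -1 to 1.

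**The concern.** The cut-offs, the filter and the band all belong to the usual signed fold-change scale, on which a halving is -2 and the interval between -1 and 1 is empty. The conversion rule cannot produce that scale. It leaves all ratios below 1 in the interval from 0 to 1, which is the range the filter discards.

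The loss is one-sided. A program that follows the text would list only ratios above 1 in Tables 6.12 and 6.13, and Table 6.11 would count no probeset as lower. Someone reading those three tables alone would see a one-directional picture produced by the derivation and not by the data.

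**Working it through.** The SAP states no numerical result here, so there is none to reproduce. The check is to run the rule as written.

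**Inputs, all from the SAP.** Response on the log2 scale, ratio taken after back-transformation, and the two-branch rule (Section 10.1.3.1). Cut-offs 1.5 and -1.5, fallback -1.25 and 1.5, and the -1 to 1 filter (Section 12.10.11).

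**Step 1: sign of the ratio.** With d the log2 difference in adjusted means, ratio r = 2^d. This is above 0 for every d, so the branch for r < 0 is never reached and fold change = r always.

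**Step 2: values.**

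| d | r = 2^d | Rule as written | Within -1 to 1? | Split at 1 |
|---|---|---|---|---|
| -3 | 0.125 | 0.125 | yes | -8 |
| -2 | 0.25 | 0.25 | yes | -4 |
| -1 | 0.5 | 0.5 | yes | -2 |
| -0.585 | 0.667 | 0.667 | yes | -1.5 |
| -0.322 | 0.8 | 0.8 | yes | -1.25 |
| 1 | 2 | 2 | no | 2 |
| 2 | 4 | 4 | no | 4 |

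**Step 3: cut-offs.** On the signed scale, -1/r < -1.5 means r < 1/1.5 = 0.667, and -1/r < -1.25 means r < 1/1.25 = 0.8. The written rule gives a negative value for no r, so neither lower category can be filled. The switch to the fallback then depends on increases alone. Because the upper cut-off is 1.5 both before and after the switch, the fallback would add nothing.

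**Step 4: filter and band.** Every r below 1 lies between 0 and 1. It is therefore removed from Table 6.12 and, among the significant blood probesets, from Table 6.13. In Figure 6.19 it is still plotted, but inside the band.

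**Step 5: could ratio mean the log2 difference?** Section 10.1.3.1 says otherwise, and the rule would still fail. A halving (d = -1) would give -1/(-1) = 1, a fourfold fall (d = -2) would give 0.5, and a doubling (d = 1) would give 1 instead of 2. Since -1 divided by a negative number is positive, no input gives a negative fold change.

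**Step 6: illustration.** I drew 53,617 log2 differences, the SAP's probeset count, from a standard normal distribution (my assumption). Of these, 27,007 were below 0. The written rule gave 0 negative fold changes, and the filter removed all 27,007 reductions and no increases. With the split at 1, all 27,007 were negative, 15,103 were below -1.5, and none fell strictly between -1 and 1. The count above 1.5 was 14,684 under both rules.

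**The case against.** The strongest reply is that this is an obvious slip in exploratory text. The signed cut-offs and the Figure 6.19 band show what was meant, the conversion is worded as something that can be done, and a competent programmer would probably split at 1 unprompted. Tables 6.11 to 6.13 and Figure 6.19 are SAC2 deliverables, after the final statistical analysis. Model estimates, confidence intervals on the log2 scale and FDR-adjusted p-values do not pass through the rule. Ratios below 1 remain visible in Figure 6.19, and lower expression remains visible in Table 6.10, Figures 6.17 and 6.18, Listings 76, 82 and 83, and the outputs that Section 10.1.3.1 promises for all analysed probesets. All of this stands and sets the severity. It does not make the rule right: nothing in the plan corrects it, and silent correction means departing from the written derivation.

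Three stronger inferences are tempting, and the document does not support them.

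- A reader might infer that the tables would hide inhibition by the drug. The fold change here compares randomised treatments, whereas the SAP defines percentage inhibition as a within-participant reduction from baseline. A ratio below 1 means lower expression than in the placebo group, which is a different quantity.
- The filter note also stands on Table 6.15, whose model is fitted "with percentage inhibition as the response variable", and might look misplaced there. It can equally be read as choosing rows by each probeset's fold change, since the percentage inhibition analysis covers selected probesets.
- The exponential expression for percentage target engagement in Section 10.1.3.1 looks inconsistent with the simpler form beside it. A sign or bracket may have been lost when the PDF was read, and the usable form appears both there and in Section 12.6.5. At most it deserves a check against the source.

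**Conclusion.** The rule is wrong as written, and this follows by deduction from the positivity of a back-transformed ratio. It needs no assumption about the data. Followed literally, the lower category of Table 6.11 is always empty, and all ratios below 1 leave Tables 6.12 and 6.13. How many rows that affects depends on the results. The simulated counts only illustrate the mechanism.

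The severity is minor. The analyses are exploratory, no primary or secondary conclusion depends on them, and the intended convention can be recognised from the rest of the plan.

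**What to change.** In Section 10.1.3.1, write: if ratio ≥ 1, fold change = ratio; if ratio < 1, fold change = -1/ratio. State that confidence limits are converted by the same rule, so that limits of 0.8 and 1.25 on the ratio scale become -1.25 and 1.25.

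In Section 12.10.11, delete the -1 to 1 filter from Tables 6.12 and 6.13, because nothing lies strictly inside that range once the split is at 1. If the aim was to suppress small effects, restate it with a threshold beyond 1. The cut-offs of Table 6.11 and the band of Figure 6.19 then work as they stand. Leave the note on Table 6.15 in place, and check the exponential target-engagement expression against the source document.

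The cost is one corrected formula and two programming notes, edited before the exploratory displays are programmed. No new data or analysis is needed.
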